1.1 Title

Oral Rivaroxaban for the Treatment of Symptomatic Venous Thromboembolism ([EINSTEIN PE](#))

1.2 Intended aim(s)

To compare the risk of symptomatic, recurrent venous thromboembolism (VTE) in patients with acute, symptomatic pulmonary embolism (PE) with or without deep vein thrombosis for rivaroxaban versus standard therapy of warfarin.

1.3 Primary endpoint for replication

The primary outcome of the study was symptomatic, recurrent VTE

1.4 Required power for primary endpoint and noninferiority margin (if applicable)

Assuming a noninferiority margin of 2.0, it was determined that about 3,000 patients would be needed to achieve 90% power to conclude noninferiority of rivaroxaban over standard therapy at two-sided alpha of 0.05.

1.5 Secondary endpoint for replication (assay sensitivity) and RCT finding

Major bleeding; RR = 0.90 (95% CI 0.76–1.07)

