6.3.1 Outcome variables

Primary Effectiveness outcomes of interest: (definitions provided in **Appendix A**):

- **Primary Outcome:** VTE

Safety outcomes of interest:

1. Major bleeding

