Appendix A

Trial Name (with web links)	EINSTEIN PE
Trial Name (with pdf links)	EINSTEIN PE
NCT	NCT00439777
Therapeutic Area	Cardiology/Vascular Diseases
Study batch	NOACs
Brand Name	Xarelto
Generic Name	Rivaroxaban
Sponsor	Bayer Johnson & Johnson Pharmaceutical Research & Development, L.L.C
Year	2012
Measurable endpoint	Percentage of Participants With Symptomatic Recurrent Venous Thromboembolism [VTE] (i.e. the Composite of Recurrent Deep Vein Thrombosis [DVT] or Fatal or Non-fatal Pulmonary Embolism [PE]) Until the Intended End of Study Treatment
Exposure	Rivaroxaban
Comparator	Enoxaparin/VKA
Population	Patients of legal age who had acute symptomatic pulmonary embolism with or without deep-vein thrombosis
Trial finding	HR = 1.12 (95% CI 0.75 to 1.68)
No. of Patients	4,832 (2,419 in exposed arm)
Non-inferiority margin	HR = 2.0
Assay Sens. Endpoint (from trial)	Percentage of Participants With the Composite Variable Comprising Recurrent DVT, Non-fatal PE and All Cause Mortality Until the Intended End of Study Treatment
Finding for potential Assay Sens. Outcome from trial-	HR = 0.85 (95% CI 0.63 to 1.14)
Power	0.90. Assuming equal efficacy, a total of 88 events was calculated to give a power of 90% to prove that rivaroxaban is at least as effective as the comparator, considering a non-inferiority upper CI margin for the hazard ratio of 2.0 (two-sided $\alpha=0.05$). A mean incidence for the primary efficacy outcome of 3% was expected and an enrollment of at least 3000 patients was necessary

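### The Section 1.5 major-bleeding benchmark implies roughly 450 to 560 trial events, so it probably belongs to a broader bleeding endpoint; Appendix A also names a different assay-sensitivity target

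*Combined protocol and SAP*

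**What the plan says.** Section 1.5 gives the secondary endpoint for replication, identified there as the assay-sensitivity endpoint, together with the trial's finding: "Major bleeding; RR = 0.90 (95% CI 0.76–1.07". Section 6.3.1 then lists "Major bleeding" as the safety outcome of the replication.

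The trial summary table in Appendix A gives the trial size as "4,832 (2,419 in exposed arm". In its assay-sensitivity rows it names a different endpoint, the composite of recurrent deep vein thrombosis, non-fatal pulmonary embolism and death from any cause, with the result "HR = 0.85 (95% CI 0.63 to 1.14". It does not mention bleeding there.

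The Major Bleeding code list in Appendix A accepts inpatient diagnosis codes in any position. Besides intracranial and gastrointestinal haemorrhage it includes epistaxis, microscopic hematuria and K56.60, unspecified intestinal obstruction.

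Nowhere do the documents give the trial's number of bleeds, its definition of major bleeding, or any second bleeding result.

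**The concern.** The confidence interval of a ratio largely fixes how many events lie behind it. The interval in Section 1.5 is narrow: it requires several times as many events as the trial's recurrent VTE result, and about three times as many as VTE and death combined. That fits poorly with an endpoint restricted to major bleeds and fits easily with one that also counts lesser bleeds.

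The benchmark is what the bleeding result of the replication will be read against. If the 0.90 belongs to a wider bleeding category, agreement or disagreement with it says little about whether the database study recovers the trial's effect on major bleeding. The reader also cannot tell which result is the assay-sensitivity target, because Section 1.5 and Appendix A name different ones. Section 13 shows no date for the comparative analyses. A correction made now is routine; one made after results are seen would look post hoc.

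**Working it through.** **Inputs.** Bleeding ratio 0.90, limits 0.76 and 1.07 (Section 1.5). Trial size 4,832, with 2,419 exposed and therefore 2,413 comparator, about 1:1 (Appendix A). Recurrent VTE, HR 1.12, limits 0.75 and 1.68 (Appendix A). Composite with death, HR 0.85, limits 0.63 and 1.14 (Appendix A). Margin and alpha: "Assuming a noninferiority margin of 2.0" and "two-sided alpha of 0.05" (Section 1.4).

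**Step 1: reproduce the plan's own figures.** With 1:1 arms, the variance of a log hazard ratio is about 4/events.

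- Appendix A reports that "a total of 88 events was calculated to give a power of 90" per cent. The formula gives 4 × (1.960 + 1.282)² / (ln 2)² = 87.5, rounded up to 88. This also fits "A mean incidence for the primary efficacy outcome of 3% was expected": 3% of 3,000 is 90 events.
- The same variance reproduces all eight power values in Sections 8 and 10. For Optum in Section 10, Φ(√57.57/2 × ln(2/1.12) − 1.96) = 0.5947, as printed.

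So this is the variance model the plan itself uses.

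**Step 2: invert it.** SE = ln(upper/lower)/3.92, and events = 4/SE². For bleeding, SE = ln(1.07/0.76)/3.92 = 0.0873 and events = 4/0.0873² ≈ 525.

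Section 1.5 labels the measure RR, so the strict risk-ratio variance is also needed: SE² = 1/a − 1/2,419 + 1/b − 1/2,413, where a and b are the events in the two arms. With a ratio of 0.90 this gives a ≈ 225 and b ≈ 250, in total 475. The hazard-ratio reading is reasonable because Section 1.6 labels as RR the 1.12 that Appendix A calls a hazard ratio. Both readings are shown, with percentages of 4,832.

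| Trial result | Limits | SE (log) | Events, hazard ratio | Events, strict risk ratio |
|---|---|---|---|---|
| Bleeding | 0.76–1.07 | 0.0873 | 525 (10.9%) | 475 (9.8%) |
| Recurrent VTE | 0.75–1.68 | 0.2057 | 94.5 (2.0%) | 93 (1.9%) |
| Composite with death | 0.63–1.14 | 0.1513 | 175 (3.6%) | 170 (3.5%) |

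**Step 3: rounding and arm sizes.** Moving each bleeding limit by ±0.005 gives 492 to 561 events on the hazard-ratio reading and 448 to 504 on the risk-ratio reading. The range is therefore about 450 to 560, or 9.3% to 11.6% of patients. Using the actual 2,419/2,413 split on the hazard-ratio reading gives 527 (about 250 against 277).

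**Step 4: compare.** On the hazard-ratio reading, bleeding has 525/94.5 = 5.6 times the VTE events and 525/175 = 3.0 times the composite events. On the risk-ratio reading the multiples are 475/93 = 5.1 and 475/170 = 2.8. Section 1.6 prints the upper VTE limit as 1.58, not 1.68. With 1.58, VTE would have about 111 events and the multiple would be 525/111 = 4.7.

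**Step 5: the reverse direction.** With a ratio of 0.90, the limits are 0.90 × exp(±1.96 × 2/√events):

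- 100 events: 0.61 to 1.33
- 175 events: 0.67 to 1.21
- 200 events: 0.68 to 1.19
- 525 events: 0.76 to 1.07, as printed

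**Step 6: is it a typing error?** The geometric midpoint of 0.76 and 1.07 is 0.902, which agrees with 0.90. One mistyped limit would normally break that agreement. In Section 1.6, for example, 0.75 and 1.58 have midpoint 1.09 against a stated 1.12. The bleeding row is coherent as a result; it is the label that does not sit well with it.

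**The case against.** The strongest reply is that the key step is inference. VTE and death are efficacy outcomes and set no arithmetic ceiling on bleeding in anticoagulated patients. Without the trial's bleeding count or definition, the documents cannot show that some 10% of patients with major bleeding is impossible. This stands. A reader might infer that the row is proven to be mislabelled, or that benchmark and measured outcome are established to be different clinical endpoints. The documents support neither; they support a strong suspicion and a source check.

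Second, the RR label permits the strict risk-ratio reading, which lowers the count to about 475. This also stands, and the range above covers it. The direction does not change.

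Third, a reader might infer that the replication outcome is a narrow one because it uses inpatient codes only. It is restricted by setting but broad by type of bleed, since it takes any diagnosis position and includes epistaxis and microscopic hematuria. Swapping in a major-bleeding-only benchmark while leaving the list alone could therefore create a new mismatch. This stands, and it shapes the fix.

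Fourth, a reader might infer that a result away from 0.90 would be declared a failed replication. The plan states no success rule for bleeding, so that consequence cannot be asserted. What remains is that any comparison with 0.90 would be hard to interpret.

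**Conclusion.** The point holds as a benchmark that needs verification, plus a contradiction that needs reconciling. The interval in Section 1.5 implies about 450 to 560 events (9% to 12% of 4,832), around five times the recurrent VTE count and three times the composite with death. The most likely explanation is a broader bleeding endpoint carrying the major-bleeding label.

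The calculation assumes a Wald-type 95% interval on the log scale, about 1:1 allocation, and that the row comes from the trial's own 4,832 patients. Confidence is high for the event count and moderate, on the documents alone, for the mislabelling.

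The conflict between Section 1.5 and Appendix A over the assay-sensitivity endpoint rests on no assumption. The primary VTE non-inferiority analysis and its power calculations do not use the bleeding figure and are unaffected.

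**What to change.** Before the comparative analysis is run:

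1. Check against the trial report which endpoint the 0.90 (0.76–1.07) row belongs to. Either replace it with the trial's estimate for major bleeding or relabel it. Print the trial event count and the type of ratio beside it.
2. Reconcile Section 1.5 with Appendix A so that one assay-sensitivity endpoint and one result are named throughout.
3. Align the Appendix A Major Bleeding code list with the benchmark chosen, so that the Section 6.3.1 outcome is compared with a like-for-like trial estimate. In particular, justify or revise the any-position rule and the entries for epistaxis, microscopic hematuria and K56.60. If the benchmark proves to be a broader category, say how bleeds outside hospital are to be handled.

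Items 1 and 2 cost one source check and a few corrected lines. Item 3 costs a review of one code list and, if it changes, reprogramming of one outcome. No new data are needed.

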1.6 Trial estimate

RR = 1.12 (95% CI 0.75-1.58) comparing rivaroxaban vs standard therapy (Agnelli et al., 2012)

2. Person responsible for implementation of replication in Aetion

[name] implemented the study design in the Aetion Evidence Platform. She is not responsible for the validity of the design and analytic choices. All implementation steps are recorded and the implementation history is archived in the platform.

3. Data Source(s)

[figure not shown]
Optum, MarketScan, Medicare

4. Study Design Diagram

The study design diagram visualizes key aspects of the longitudinal study design for expedited review.

Figure 1

Design Diagram – EINSTEIN PE TRIAL REPLICATION

5. Cohort Identification

5.1 Cohort Summary

This study will involve a new user, parallel group, propensity score-matched, retrospective cohort study design comparing rivaroxaban to warfarin users. The patients will be required to have continuous enrollment during a baseline period of 180 days before initiation of rivaroxaban or warfarin (index date). We will restrict the analyses to patients with a diagnosis of PE.

5.2 Important steps for cohort formation

New use of rivaroxaban, exposure, and warfarin, comparator, is defined as no use of either therapy in 180 days prior to index date.

5.2.1 Eligible cohort entry dates

Market availability of rivaroxaban in the U.S. prevention of venous thromboembolism after orthopedic surgery started on July 01, 2011

- For Medicare: July 01, 2011– December 31, 2017 (end of available data)
- For Marketscan: July 01, 2011 – December 31, 2018 (end of available data)
- For Optum: July 01, 2011 – March 31, 2020 (end of available data)

5.2.2 Specify inclusion/exclusion criteria for cohort entry and define the index date.

Inclusion and exclusion criteria were adapted from the trial as closely as possible. Definitions for all inclusion/exclusion are provided in **Appendix A** and are summarized in the flowcharts below.

5.3 Flowchart of the study cohort assembly

	Optum		Truven		Medicare	
	Less Excluded Patients	Remaining Patients	Less Excluded Patients	Remaining Patients	Less Excluded Patients	Remaining Patients
All patients		78,202,636		200,203,908		6,886,908
Did not meet cohort entry criteria	-77,207,180	995,456	-199,008,369	1,195,539	-1,964,276	4,922,632

Excluded due to insufficient enrollment	-127,407	868,049	-98,795	1,096,744	-1,580,438	3,342,194
Excluded due to prior use of referent	-508,219	359,830	-676,683	420,061	-2,158,638	1,183,556
Excluded due to prior use of exposure and because patient qualified in >1 exposure category	-216,850	142,980	-210,419	209,642	-680,443	503,113
Excluded based on Age < 65 (Medicare only)	-	-	-	-	-55358	447,755
Excluded based on Age, Gender, and Use of other NOACs (dabigatran, apixaban, edoxaban)	-5393	137,587	-4262	205,380	-17641	430,114
Excluded based on Inclusion 1 - Pulmonary embolism	-117,221	20,366	-169,963	35,417	-372,047	58,067
Excluded based on Exclusion 1 - Age and Exclusion 2 - Thrombectomy or insertion of a caval filter	-196	20,170	-274	35,143	-546	57,521
Excluded based on Exclusion 3 - Other Indications for VKA	-1836	18,334	-1,617	33,526	-6,213	51,308
Excluded based on Exclusion 6 - KD stage 4/5/ESRD	-56	18,278	-42	33,484	-136	51,172
Excluded based on Exclusion 7 - Significant liver disease	-426	17,852	-505	32,979	-900	50,272
Excluded based on Exclusion 8 - Bacterial endocarditis and Exclusion 9 - CCI >= 10	-154	17,698	-114	32,865	-398	49,874
Excluded based on Exclusion 10 - Active bleeding or high risk for bleeding	-262	17,436	-334	32,531	-670	49,204
Excluded based on Exclusion 11 - malignant hypertension	-33	17,403	-42	32,489	-57	49,147
Excluded based on Exclusion 12 - Pregnancy and Exclusion 14 - strong CYP3A4 inhibitors or strong CYP3A4 inducers	-19	17,384	-44	32,445	-29	49,118
Final cohort		17,384		32,445		49,118

6. Variables

6.1 Exposure-related variables:

Study drug:

The study exposure of interest is initiation of rivaroxaban. New initiation will be defined by no use of rivaroxaban or warfarin in the prior 6 months before treatment initiation (washout period).

Comparator:

New initiators of warfarin, defined by no use of rivaroxaban or warfarin in the prior 6 months.

6.2 Covariates:

- Age
- Sex
- Combined Comorbidity Index (CCI), measured over the baseline covariate assessment period, defined as 180 days prior to and including index date

Covariates listed above represent only a small subset of covariates that will ultimately be controlled for in the design and analysis. We use the covariates above only for initial feasibility analyses to judge whether there is likely to be sufficient overlap between treatment groups to proceed with the study. Remaining covariates are defined only after the study has passed the initial feasibility analysis and the initial power assessment and are listed in Table 1 (**Appendix B**).

6.3 Outcome variables and study follow-up:

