6.3.2 Study follow-up

Both as-treated (AT) and intention-to-treat (ITT) analyses will be conducted with treatment defined as the index drug on the day of cohort entry. Because adherence in the real-world databases is expected to be much worse than in the trial, the AT analysis is the **primary** analysis, as it targets the relative hazard of outcomes on treatment.

For the AT analyses, the follow-up will start the day after initiation of rivaroxaban and comparator and will continue until the earliest date of the following events:

- The first occurrence of the outcome of interest, unless otherwise specified for selected outcomes,
- The date of end of continuous registration in the database,
- End of the study period,
- Measured death event occurs,
- Nursing home admission
 - Nursing home admissions are considered a censoring event because the data sources utilized typically provide little to no data on a patient, particularly on drug utilization, after admission. We will utilize this as an exclusion reason for cohorts for the same reason.
- The date of drug discontinuation, defined as the date of the last continuous treatment episode of the index drug (rivaroxaban and comparator) plus a defined grace period (i.e., 10 days after the end of the last prescription's days' supply in main analyses).
- The date of augmentation or switching from exposure to comparator or vice versa or augmentation/switching to any other NOAC (e.g. switching from rivaroxaban to apixaban would be a censoring event);
 - A dosage change on the index treatment does not fulfill this criterion
 - An added treatment that is not part of the exposure or comparator group does not fulfill this criterion

For the intention-to-treat (ITT) analyses, the censoring based on the augmentation/switching and treatment discontinuation will be replaced with a maximum allowed follow-up time of 365 days.

7. Initial Feasibility Analysis

Action report name:

Optum- <https://bwh-dope.aetion.com/projects/details/1527/rwrs/66276>

MarketScan- <https://bwh-dope.aetion.com/projects/details/1653/rwrs/66277>

Medicare- <https://bwh-dope.aetion.com/projects/details/1525/rwrs/67892>

Date conducted: 02/24/2021

Complete Aetion feasibility analysis using age, sex, and CCI as the only covariates and the primary endpoint (Section 6.3.1) as the outcome. No measures of association will be computed nor will incidence rates stratified by treatment group.

- Report patient characteristics by treatment group

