Power	0.967396851

- MarketScan

Non-inferiority Analysis	
Number of patients matched	18,776
Reference	9,388
Exposed	9,388
Risk per 1,000 patients	14.88
Assumed HR from RCT	1.12
Alpha (2-sided)	0.05
Non-inferiority margin	2
Number of events expected	279.38688
Power	0.998048094

○ Medicare

Non-inferiority Analysis	
Number of patients matched	32,386
Reference	16,193
Exposed	16,193
Risk per 1,000 patients	13.64
Assumed HR from RCT	1.12
Alpha (2-sided)	0.05
Non-inferiority margin	2
Number of events expected	441.74504
Power	0.999982118

- Stop analyses until balance and final power assessment are reviewed by primary investigators, FDA, and assigned members of advisory board.

Reviewed by PI:		Date reviewed:	
Reviewed by FDA:		Date reviewed:	
Reasons for stopping analysis (if required):			

9. Balance Assessment

Action report links:

Optum: <https://bwh-dope.aetion.com/projects/details/1527/rwrs/67705>

Marketscan: <https://bwh-dope.aetion.com/projects/details/1653/rwrs/67706>

Medicare: <https://bwh-dope.aetion.com/projects/details/1525/rwrs/67894>

Date conducted: 3/28/2021

After review of initial feasibility and power analyses, complete creation of the remaining covariates from Section 6.2. Again, using the dummy outcome of a 90-day gap in database enrollment, complete a 1:1 PS-matched analysis. The PS should include the complete list of covariates.

- Provide plot of PS distributions stratified by treatment group.

Note- Please refer to **Appendix B**.

- Report covariate balance after matching.

Note- Please refer to **Appendix B**.

- Report reasons for censoring by treatment group.

	Overall	Referent	Exposure
Dummy outcome	0 (0.0%)	0 (0.0%)	0 (0.0%)
Death	477 (1.50%)	218 (1.37%)	259 (1.63%)
Start of an additional exposure	1,584 (4.98%)	1,023 (6.44 %)	561 (3.53%)
End of index exposure	23,632 (74.35%)	11,350 (71.42%)	12,282 (77.28%)
Specified date reached	1,617 (5.09%)	875 (5.51%)	742 (4.67%)
End of patient enrollment	2,079 (6.54%)	1,046 (6.58%)	1,033 (6.50%)
Switch to other NOACs (for censoring) + nursing home admission	2,397 (7.54%)	1,381 (8.69%)	1,016 (6.39%)

- Report follow-up time by treatment group.

Median Follow-Up Time (Days) [IQR]			
Patient Group	Optum	MarketScan	Medicare
Overall Patient Population	70 [36-174]	91 [38-184]	97 [38-195]
Referent	75 [38-173]	92 [40-178]	100 [41-199]
Exposure	65 [33-175]	91 [38-188]	88 [38-190]

10. Final Power Assessment

Date conducted: 03/28/2021

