Mean Copay for per prescription cost (charges in U.S. \$) (180-1 day prior)												
...mean (sd)	23.14 (33.19)	20.04 (30.76)	0.10	16.79 (25.44)	13.74 (31.23)	0.11	110.77 (126.57)	109.04 (134.46)	0.01	64.06 (91.02)	63.21 (98.08)	0.00
...Missing; n (%)	801 (7.3%)	538 (8.3%)	-0.04	1,853 (8.0%)	874 (9.3%)	-0.05	996 (3.0%)	523 (3.2%)	-0.01	3650 (5.5%)	1935 (6.0%)	-0.02

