...mean (sd)	0.12 (0.36)	0.16 (0.42)	-0.10	0.13 (0.38)	0.14 (0.39)	-0.03	0.14 (0.36)	0.17 (0.40)	-0.08	0.13 (0.37)	0.16 (0.40)	0.00
Number of CRP, high-sensitivity CRP tests												
...mean (sd)	0.10 (0.47)	0.12 (0.53)	-0.04	0.09 (0.48)	0.09 (0.45)	0.00	0.13 (0.55)	0.14 (0.57)	-0.02	0.11 (0.51)	0.12 (0.53)	0.00
Number of PT or aPTT tests												
...mean (sd)	0.66 (1.77)	0.58 (1.39)	0.05	0.58 (1.48)	0.47 (1.22)	0.08	0.38 (0.91)	0.35 (0.74)	0.04	0.49 (1.29)	0.43 (1.05)	0.00
Number of Bleeding time tests												
...mean (sd)	0.00 (0.02)	0.00 (0.01)	0.00	0.00 (0.02)	0.00 (0.01)	0.00	0.00 (0.03)	0.00 (0.02)	0.00	0.00 (0.03)	0.00 (0.02)	0.00
HAS-BLED Score (ICD-9 and ICD-10), 180 days												
...mean (sd)	2.68 (1.05)	2.55 (1.03)	0.12	2.28 (0.98)	2.21 (0.95)	0.07	3.43 (0.79)	3.39 (0.80)	0.05	2.91 (0.90)	2.88 (0.90)	0.00
N of Generic name drugs												
...mean (sd)	15.36 (13.41)	13.47 (14.05)	0.14	13.18 (11.45)	11.66 (11.95)	0.13	18.30 (13.64)	16.35 (14.30)	0.14	16.06 (12.89)	14.40 (13.60)	0.00
N of Brand name drugs												
...mean (sd)	2.98 (4.53)	3.58 (3.90)	-0.14	3.30 (4.45)	3.75 (3.79)	-0.11	3.22 (4.77)	3.92 (4.27)	-0.15	3.21 (4.62)	3.80 (4.06)	0.00
Use of clopidogrel; n (%)	259 (2.4%)	122 (1.9%)	0.03	499 (2.2%)	145 (1.5%)	0.05	1,670 (5.1%)	716 (4.4%)	0.03	2428 (3.6%)	983 (3.1%)	0.03
Systemic embolism; n (%)	221 (2.0%)	112 (1.7%)	0.02	404 (1.8%)	141 (1.5%)	0.02	462 (1.4%)	200 (1.2%)	0.02	1087 (1.6%)	453 (1.4%)	0.02
DVT; n (%)	5,150 (47.1%)	3,078 (47.7%)	-0.01	10,806 (46.9%)	4,578 (48.7%)	-0.04	14,349 (43.6%)	6,958 (42.9%)	0.01	30305 (45.3%)	14614 (45.6%)	-0.01
Post-thrombotic syndrome; n (%)	** (0.1%)	** (0.1%)	#DIV/0!	14 (0.1%)	** (0.1%)	#DIV/0!	21 (0.1%)	12 (0.1%)	#DIV/0!	14 (0.1%)	** (0.1%)	0.00
PE; n (%)	10,931 (100.0%)	6,448 (100.0%)	#DIV/0!	23,030 (100.0%)	9,398 (99.9%)	0.04	32,865 (99.9%)	16,217 (100.0%)	-0.04	66826 (99.9%)	32063 (100.0%)	-0.04
Coagulation defects; n (%)	285 (2.6%)	123 (1.9%)	#DIV/0!	654 (2.8%)	211 (2.2%)	#DIV/0!	579 (1.8%)	213 (1.3%)	#DIV/0!	654 (2.8%)	211 (2.2%)	0.04
Diabetes: 1 inpatient or 2 outpatient claims within 183 days; n (%)	2,243 (20.5%)	1,185 (18.4%)	0.05	3,626 (15.7%)	1,408 (15.0%)	0.02	8,179 (24.9%)	3,686 (22.7%)	0.05	14048 (21.0%)	6279 (19.6%)	0.03
Intracranial or retroperitoneal hemorrhage: 1 inpatient or 2 outpatient claims within 183 days; n (%)												
** (0.0%)	** (0.0%)	#DIV/0!	** (0.0%)	** (0.0%)	#DIV/0!	15 (0.0%)	** (0.0%)	#DIV/0!	#VALUE!	#VALUE!	#VALUE!	#VALUE!

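### As written, the baseline window includes the index date, so the brand and generic drug counts in the propensity score would include the study dispensing and partly encode exposure

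*Combined protocol and SAP*

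**What the plan says.** - **Window.** Section 6.2 names the study's baseline covariate period at the comorbidity index entry: "measured over the baseline covariate assessment period, defined as 180 days prior to and including index date". The remaining covariates "are listed in Table 1", that is, in Appendix B.
- **New use.** Under Section 5.2, new use of either study drug "is defined as no use of either therapy in 180 days prior to index date". The index drug can therefore enter a baseline count only on the index date.
- **Follow-up.** In the as-treated analysis of Section 6.3.2, "the follow-up will start the day after initiation of rivaroxaban and comparator", so the index date itself is left to baseline.
- **Propensity score.** Section 9 instructs: "The PS should include the complete list of covariates". Appendix B has a block of variables marked for the score, and the rows "N of Brand name drugs" and "N of Generic name drugs" stand in it without any window label.
- **Contrast.** In the same block, the copay row is limited to "180-1 day prior", and one ticagrelor row is tied to the cohort entry date. Departures from the general window are thus labelled at least sometimes.

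**The concern.** A drug count that includes the index dispensing contains the treatment. Every rivaroxaban starter gains one in one column, and most warfarin starters gain one in the other. To balance such a count, the match has to pair rivaroxaban patients with warfarin patients who had about one more other brand fill and fewer other generic fills. The balance table would then report agreement on a quantity that is not pre-treatment history, and would conceal a difference in the quantity that is. The reviewers at the Section 10 stop rely on that table in deciding whether to go on to the outcome comparison.

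**Working it through.** **Inputs.** Means (SD) from Appendix B, warfarin then rivaroxaban.

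| | Optum | MarketScan | Medicare |
|---|---|---|---|
| Brand, before matching | 2.98 (4.53), 3.58 (3.90) | 3.30 (4.45), 3.75 (3.79) | 3.22 (4.77), 3.92 (4.27) |
| Generic, before matching | 15.36 (13.41), 13.47 (14.05) | 13.18 (11.45), 11.66 (11.95) | 18.30 (13.64), 16.35 (14.30) |
| Brand, after matching | 3.36 (5.57), 3.32 (3.34) | 3.47 (5.19), 3.52 (3.38) | 3.69 (5.67), 3.68 (3.75) |
| Generic, after matching | 15.55 (13.45), 15.82 (15.34) | 12.64 (11.01), 12.67 (12.69) | 17.54 (13.04), 18.06 (15.69) |

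**Step 1: reproduce the plan's figures.** SMD = (warfarin mean - rivaroxaban mean) / sqrt((SD0² + SD1²)/2). Before matching, brand gives -0.142, -0.109, -0.155 (printed -0.14, -0.11, -0.15) and generic gives 0.138, 0.130, 0.140 (printed 0.14, 0.13, 0.14). The database columns reproduce. The pooled column does not: it prints 0.00 for both rows, whereas the pooled means and SDs give -0.136 (brand) and 0.125 (generic).

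**Step 2: what is being counted.** For Optum warfarin users, brand plus generic is 2.98 + 15.36 = 18.34, against 8.99 distinct medications. The rows therefore appear to count fills.

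**Step 3: do the unmatched means fit inclusion?** Rivaroxaban starters have fewer generic fills (-1.89, -1.52, -1.95) and fewer distinct medications (8.21 vs 8.99, 8.08 vs 8.84, 9.34 vs 10.02), yet more brand fills (+0.60, +0.45, +0.70). Removing one brand fill per rivaroxaban starter turns the last set into -0.40, -0.55, -0.30. Brand share of all fills, rivaroxaban vs warfarin, is 21.0% vs 16.2%, 24.3% vs 20.0% and 19.3% vs 15.0%. After removing one index fill from each arm it is 16.1% vs 17.2%, 19.1% vs 21.3% and 15.2% vs 15.7%. The pattern is what inclusion would produce.

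**Step 4: matched counts net of the index fill.** Subtract 1 from the rivaroxaban brand mean and 1 from the warfarin generic mean; the SDs are unchanged by a constant.

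| | Optum | MarketScan | Medicare |
|---|---|---|---|
| Brand, warfarin vs rivaroxaban | 3.36 vs 2.32 | 3.47 vs 2.52 | 3.69 vs 2.68 |
| Brand SMD | 1.04/4.592 = 0.226 | 0.95/4.380 = 0.217 | 1.01/4.807 = 0.210 |
| Brand SMD with index fill left in | 0.009 | -0.011 | 0.002 |
| Generic, warfarin vs rivaroxaban | 14.55 vs 15.82 | 11.64 vs 12.67 | 16.54 vs 18.06 |
| Generic SMD | -0.088 | -0.087 | -0.105 |
| Brand share, warfarin vs rivaroxaban | 18.8% vs 12.8% | 23.0% vs 16.6% | 18.2% vs 12.9% |

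**Step 5: sensitivity.** If 90% of warfarin index fills are generic and the rest brand (SDs held as printed), the matched brand SMD is 0.205, 0.194, 0.189. At 80% it is 0.183, 0.171, 0.169.

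**Step 6: total fills.** Matched brand plus generic, warfarin vs rivaroxaban, is 18.91 vs 19.14, 16.11 vs 16.19 and 21.23 vs 21.74. Removing one fill from each arm leaves the gaps at 0.23, 0.08 and 0.51, so the total stays close.

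**The case against.** The strongest objection is that inclusion is inferred. The window is written out at the comorbidity index entry only, and the two counts are not defined in the text shown. Windows in Appendix B are set row by row, and the design diagram and the opening of Appendix B, which could not be read in the text available, may state one. Brand or generic status of the index fills is also an assumption; the brand name in Appendix A describes the trial product, not a claims classification. This stands, and it makes the point conditional.

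A reader might also infer more than the documents support:

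- **That baseline medication burden is unbalanced.** Step 6 shows that it is not. The distinct-prescription count gains one in both arms, so it is not differentially affected; it matches at 9.05 vs 9.04, 8.49 vs 8.53 and 9.74 vs 9.85.
- **That the unequal SDs after matching prove inclusion.** Hospital days, which contain no dispensing, behave similarly: the Optum SDs go from 4.96 and 4.04 to 3.52 and 5.88 while the matched means agree (5.88 vs 5.78).
- **That these counts caused the loss of matched pairs.** Stronger separators are visible before matching: heparin use (SMD 1.34 in Optum, 1.15 in Medicare) and CHA2DS2-VASc (0.80, 0.64, 0.56). No share of the loss can be assigned to the counts.
- **That fewer distinct medications on rivaroxaban is a clean benchmark.** Part of that gap may be heparin itself (53.4% vs 3.3% in Optum).
- **That the hazard ratio is shown to be biased.** Nothing in the documents links brand/generic composition to recurrent VTE.

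**Conclusion.** The point holds in conditional form. On the plan's own window, washout and covariate instruction, and with no visible exclusion, the brand and generic counts would include the study dispensing, and the propensity score would partly match on exposure. The means in three databases are consistent with this; means and SDs cannot establish it.

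If it is so, the match hides a brand-fill difference of about one fill (SMD 0.21 to 0.23, or 0.169 to 0.205 if 80-90% of warfarin index fills are generic) and an opposite generic difference (SMD -0.087 to -0.105). The size rests on one brand fill per rivaroxaban starter, one index fill per warfarin starter, and the stated generic share. The effect is a shift in brand/generic composition. The documents support no claim about overall medication burden, matched-pair loss or the direction of the outcome estimate. The stated power figures also stand until a new match changes the matched numbers. It is worth settling because the balance table cannot reveal the problem and no outcome comparison is yet reported.

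**What to change.** In Section 6.2 and Appendix B, state the window for the brand and generic counts. Either measure both over days -180 to -1, as the copay row already does, or exclude rivaroxaban and warfarin fills from them. If the implemented counts already exclude the index fill, one sentence saying so closes the point. Otherwise refit the propensity score, re-match, and re-issue the Section 9 balance and follow-up tables and the Section 10 matched numbers and power.

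The cost is one change of covariate definition and one rerun of the match. Section 13 carries no report or date, so this can still precede the comparative analysis; done afterwards, it would be a post hoc change. The day -1 option has a small downside: other drugs first dispensed on the index date also leave the counts. Excluding only the two study drugs avoids that.
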